1.3 Research Design and Methods

This is a retrospective cohort study of women diagnosed with aggressive breast or ovarian cancer in New Jersey, New Mexico, and Colorado. This application covers the work being completed in New Jersey only. The NJSCR will identify women recently diagnosed breast and ovarian cancer who meet the following inclusion/exclusion criteria. (Table 1)

We will not include any of the following special populations:

- Adults unable to consent
- Individuals who are not yet adults (infants, children, teenagers)
- Pregnant women
- Prisoners

Table 1: Inclusion / Exclusion Criteria for NJSCR recruitment

Cancer Type	Inclusion	Exclusion
Breast Cancer survivors	Hispanic or non-Hispanic Female 21 years of age or older English or Spanish-speaking Breast cancer history = breast cancer at the age or before age 50 OR triple negative breast cancer at or before age 60 OR two or more primary breast cancers Primary Cancer dx'd prior to breast cancer is OK Primary tumor dx'd after breast cancer is OK	Have had prior genetic counseling or testing for hereditary breast and/or ovarian cancer Unable to give informed consent (incoherent, dementia) No access to a telephone In hospice care Incarcerated Permanent residence outside of NJ Planning on relocating out of NJ within the next year
Ovarian Cancer Survivors	Hispanic or non-Hispanic Female 21 years of age or older English or Spanish-speaking History of ovarian, fallopian, or peritoneal cancer diagnosed at any age Primary Cancer dx'd prior to ovarian cancer is OK Primary tumor dx'd after ovarian cancer is OK	Have had prior genetic counseling or testing for hereditary breast and/or ovarian cancer Unable to give informed consent (incoherent, dementia) No access to a telephone In hospice care Incarcerated Permanent residence outside of NJ Planning on relocating out of NJ within the next year

A. Research procedures:

The NJSCR will conduct patient recruitment following their established Standard Operating Procedures (NJSCR Data Repository #Pro20140000992).

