Prophylactic Measures	x		x	x	Assess uptake of and intention to get mastectomy, mammography, breast MRI, oophorectomy, CA 125, and pelvic ultrasound. Participants will also report on how much time they spent getting each procedure, how much childcare they paid for, and how many miles they had to drive.
Psychological Distress ^{167,168} : BSI anxiety ($\alpha = 0.79-0.81$); BSI depression ($\alpha = 0.84-0.85$); Short PSS ^{170,171} ($\alpha = 0.84-0.86$)	x	x	x	x	Psychological distress will be assessed using the following: anxiety and depression subscales of the Brief Symptom Inventory; ^{167,168} Short Perceived Stress Scale. ^{170,171}
Cancer Worry: The McCaul Brief Worry Scale ^{165,166} ($\alpha = 0.78$)	x	x	x	x	Three items will assess cancer worry using the McCaul Brief Worry Scale ^{165,166}
Fear of HBOC: Affect in Risk Scale ^{145,164} ($\alpha = 0.94$)	x	x	x		Fear of HBOC will be assessed using 6 items in the Affect in Risk Scale. ^{145,164}
Defensive Avoidance	x	x	x		Four items assess avoidance in thinking about personal and familial inherited cancer risk. ^{172,173}
Perceived HBOC risk for self and family ^{146,180,181} . Perceived threat and efficacy regarding HBOC: Risk Behavior Diagnosis Scale (RBDS) ^{182,183} ($\alpha = 0.76-0.92$)	x	x	x		Four items assess perceived HBOC risk for self and family ^{146,180,181} . Threat and efficacy related to HBOC is assessed using the RBDS which assesses cancer-focused EPPM constructs (perceived risk, response efficacy, self-efficacy, cancer severity). ^{182,183}
HBOC Knowledge: National Center for Human Genome Research Knowledge Scale ¹⁶⁰ ($\alpha = 0.74$)	x	x			HBOC knowledge will be assessed using items from the National Center for Human Genome Research Knowledge Scale. ¹⁶⁰ Additional items specific to breast and ovarian cancer survivors ¹⁵⁹ have been added, as well as items to assess misconceptions concerning hereditary cancer, CGRA, and genetic testing

Family Cancer History	x				Family history of cancer: relative, cancer type, age at diagnosis, etc.
Prior Access to CGRA and Genetic Testing	x				Will assess whether participants had heard about CGRA and/or were referred for CGRA and HBOC genetic testing (e.g., BRCA1/2) prior to being contacted for this study

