Physician/Health Care Provider Recommendation and Communication	x	x	x	x	Will assess whether healthcare providers have discussed participant's risk of HBOC and CGRA, and how participants feel discussing CGRA and genetic testing with health care provider.
Cancer Genetic Risk Assessment (Genetic Counseling)		x	x	x	Participants will be asked whether they have had CGRA, the provider who conducted the CGRA, and the provider's genetics training. CGRA will be medical record verified.
Cancer Genetic Risk Assessment Intention	x	x	x	x	One item will measure future intention to get cancer genetic risk assessment. In follow up surveys, this will only be asked if participant does not report uptake of CGRA
HBOC Genetic Testing Uptake		x	x	x	Participants will be asked whether they have had HBOC genetic testing, what type of genetic test they had, and the facility where the testing was done. Genetic testing will be medical record verified.
HBOC Genetic Testing Intention	x	x	x	x	One item will measure future intention to get genetic testing for HBOC. In follow up surveys, this will only be asked if participant does not report uptake of genetic testing.
Decisional conflict for CGRA: SURE Scale ^{153,154} ($\alpha = 0.86$)		x	x	x	Decisional conflict associated with the CGRA decision will be measured separately with 4 items using the SURE Scale ^{153,154}
Decisional conflict for HBOC genetic testing: Low Literacy Decisional Conflict Scale (DCS)SURE Scale ^{153,154} ($\alpha = 0.86$)			x	x	Decisional conflict associated with the HBOC gene test decision will be measured separately with 4 items using the SURE SCALE ^{153,154}
Decisional satisfaction with CGRA: Satisfaction with Decision Instrument ^{155,156} ($\alpha = 0.90$).			x	x	Decisional satisfaction will be assessed using the Satisfaction with Decision Instrument. ^{155,156} Four questions assess their personal satisfaction with their decision and three additional items assess

					how they feel about their CGRA decision in relation to their family.
Decision Regret Scale ¹⁵⁸ ($\alpha = 0.81-0.92$)			x	x	Five items will ask about regret regarding the decision to have or not have CGRA. ¹⁵⁸
CGRa and HBOC Genetic Testing Facilitators ^{42,126}	x	x	x	x	Facilitators include but are not limited to: help from family, desire to reduce risk of second cancers, and help/referrals from medical professionals.

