who desire but did not access CGRA. Evaluation of the incremental effect will be assessed by comparing the difference of the primary outcome between changed intervention arms (UC to TP/TCN; TP to TCN). For those that availed themselves of “free” CGRA provided through the study, we will describe patient preferences by study arm and other factors (e.g., age, ethnicity, residence area, education, income, literacy, psychosocial factors, and language preference). Model selection with multiple variables will be conducted using AIC and BIC approximation criteria, while including theoretically and practically relevant variables. **Aim 2** tests whether there are differences across the 3 study arms with regard to uptake of genetic testing for HBOC at 6 and 12 months. Similar to Aim 1, multivariable regression modeling approach will be performed for the binary outcome (genetic testing yes vs. no) with the main covariate of arm and other confounding variables at each time point. Then, generalized linear mixed effects model (GLMM) will be employed for the two time point outcomes, using binomial distribution with logit link function and adjusting for the correlation within the same subjects to estimate the behavior trend over time. **Aim 3** compares cognitive and affective intermediate endpoints among women in the 3 study arms and explores potential underlying theoretical mediating and moderating mechanisms that will further specify and elucidate significant 6-month and 12-month intervention effects, if such effects are observed. The study arms will be compared with regard to beliefs (threat and efficacy), informed decision making indicators (knowledge, decisional conflict, and decision regret) and emotional factors (cancer worry and fear). Arm comparisons will be based on differences in least-square mean changes from baseline to 6 months (including values from the 1-month survey) from an analysis of covariance model containing terms for study arm with baseline scores for as a covariate. Structural equation modeling (SEM) for the hypothesized meditational pathways will be conducted with the procedure of CALIS in SAS and the ‘sem’ package in R. Before the SEM, all variables in the modeling will be centered with means zero. The SEM will focus on (1) specifying structural equation models; (2) interpreting the model fit statistics and estimation results; (3) testing model with the arms; and (4) analyzing direct and indirect effects. Mediators of intervention effects include threat appraisals, response efficacy, self-efficacy, knowledge, recommendation about CGRA measured at one-month post intervention. Several indices will be used to assess the adequacy of overall model fit: Comparative Fit Index, Standardized Root Mean-Square Residual, and Root-mean Square Error-of Approximation.¹⁸⁸ The interventions may not be beneficial for all study participants. Thus, sensitivity/moderation analysis will be done to identify subgroups for which the intervention has or does not have an effect (e.g., age, diagnosis, time since diagnosis, rural/urban, education level, literacy, acculturation, language preference, close at-risk relative, household income, familism, family support of CGRA, provider recommendation, and cost, travel and time barriers). This will provide important information about subgroups who are particularly receptive or resistant to the effect of each intervention.

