Multiple imputation assumed missing at random and was based on verified CGRA within 6months and demographic information; having a primary care provider; cancer site (breast v ovarian cancer); and number of first- and second-degree relatives with cancer, as well as the a priori interaction of the intervention with potential effect modifiers: race, ethnicity, health insurance status, literacy level, and household income. Ten imputed data sets were generated using IVEware with sequential regression, and Rubin's rule was applied to combine results using SAS Proc Mianalyze. Odds ratios, CGRA percentages, and 95% CIs were conducted using SAS v9.4.

With a final sample size of at least 212 per arm and 3% of CGRA for TP or UC, the minimum detectable OR for comparisons between TCN and TP or between TCN and UC is 1.86 with 80% power and 5% overall type I error rate (2.5% for each comparison) after multiplicity adjustment.

Demographic and clinical characteristics of participants were compared among three arms using ANOVA and chi-square analysis. The mediators at baseline and 1 month were compared (within arms and between arms) using paired *t*-tests and two-sample *t*-tests; CGRA uptake at 6 months was compared using a chi-square test.

Generalized structural equation modeling (GSEM) was used for mediation analysis because CGRA uptake is a binary outcome. All 1-month cognitive and emotional mediators were controlled for baseline levels and all scores were standardized. Maximum likelihood estimation was used for estimating regression coefficients/parameters. Indirect effects were estimated, and a bootstrapping method (1,000 replications) was used to construct 95% confidence intervals.

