Age, household income, education attainments, ethnicity, health insurance, urban/rural residence, cancer type, years since diagnosis, health literacy, and family history of cancer were controlled as covariates in all regressions in GSEM. We adopted negative imputation for the outcome variable, CGRA uptake – assuming no documentation meant no uptake. Sensitivity analyses with multiple imputation for missing data were conducted, based on the assumption of missing at random. Effect estimates were derived using Rubin's rule. All analyses were performed using Strata MP 17. The Monte Carlo simulation technique, was used to examine the power and estimate the minimal detectable indirect effects. Results showed that our study has at least 80% power ($\alpha = 0.05$, two-sided) to test a minimal indirect effect of 0.37 for a single mediator and an indirect effect of 0.007-0.032 for serial mediation with two to three mediators.

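### The 6-month mediation model leaves out prior CGRA referral and awareness, and does not list baseline recommendation or intention, so its indirect effects on uptake can be biased

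*Protocol*

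**What the plan says.** **What is collected at baseline.** Protocol section 1.8.B, Table 5, marks three CGRA-specific items in the baseline column:

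- Prior access, at baseline only: "Will assess whether participants had heard about CGRA and/or were referred for CGRA and HBOC genetic testing (e.g., BRCA1/2) prior to being contacted".
- Provider recommendation and communication, at all four surveys: "Will assess whether healthcare providers have discussed participant's risk of HBOC and CGRA".
- CGRA intention, at all four surveys: "One item will measure future intention to get cancer genetic risk assessment". At follow-up it is put only to women who have not reported uptake.

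**Who is enrolled.** Table 1 in protocol section 1.3 excludes women who "Have had prior genetic counseling or testing for hereditary breast and/or ovarian cancer". It does not exclude a woman who was referred and has not yet been seen.

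**What the mediation model adjusts for.** The third SAP item fits a generalized structural equation model (GSEM) for 6-month uptake. It states: "All 1-month cognitive and emotional mediators were controlled for baseline levels and all scores were standardized". The covariate list is: "Age, household income, education attainments, ethnicity, health insurance, urban/rural residence, cancer type, years since diagnosis, health literacy, and family history of cancer were controlled". That is ten covariates, and they enter every regression. None of the three CGRA-specific baseline items is on the list.

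**Which mediators.** The SAP item does not name them. Protocol section 6.1 does: "Mediators of intervention effects include threat appraisals, response efficacy, self-efficacy, knowledge, recommendation about CGRA measured at one-month post intervention". Intention is not in that sentence, although section 1.8.B places it under cognitions and beliefs.

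**The concern.** An indirect effect is the product of two paths, arm to mediator and mediator to uptake. Randomisation covers the first path and the total effect. The second is an observational association within arms, so it needs adjustment for common causes of 1-month beliefs and 6-month uptake.

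Prior referral, an earlier provider recommendation and an existing intention to go are credible common causes. The protocol treats them that way: section 1.2 says many referred women do not follow through, section 1.8.B lists professional referral as a facilitator and recommendation as a cue to action, and section 6.1 names provider recommendation as a possible moderator.

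The schedule offers a route by which they could act beyond the baseline belief score. In the two intervention arms the 1-month survey falls 30 days after an intervention that may itself come up to 30 days after baseline. Table 5 already asks about CGRA uptake at that survey. A woman with a referral in hand could speak to her provider, read up or attend CGRA in that window.

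At stake is the mechanism statement in Aim 3. Beliefs could be credited with carrying the effect of telephone counseling and navigation (TCN) when they partly mark women who were already heading for CGRA.

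**Working it through.** **1. The omission.** This is a matter of reading. Comparing Table 5 with the covariate list:

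| Baseline item | Among the ten covariates? | Could it be covered as a mediator's own baseline? |
|---|---|---|
| Prior referral/awareness | No | No; asked only at baseline, so it has no 1-month value |
| Provider recommendation | No | Possibly; it is a protocol mediator, but classed as a cue to action rather than as cognitive or emotional |
| CGRA intention | No | Possibly; classed under cognitions, but not named as a mediator in section 6.1 |

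**2. The plan's own figures.** The SAP gives a minimum detectable indirect effect of 0.37 for one mediator and 0.007-0.032 for serial mediation. Neither can be reproduced, because no path coefficients, scale or mediator correlations are given. The protocol's uptake power figures do reproduce with 182 per arm, two-sided: 7% vs 22% at alpha 0.017 gives 95.7%, and 19% vs 34% at alpha 0.025 gives 84.5%. They serve here only to anchor the uptake rates.

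**3. Model for the bias.** All effect sizes below are assumptions. T is arm, U is prior referral (prevalence q), M0 and M1 are the mediator at baseline and 1 month, and Y is uptake.

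- M0 = 0.5(U − q) + e0, with SD(e0) = 1
- M1 = 0.5T + 0.5·M0 + g(U − q) + e1, with SD(e1) = 0.85
- logit P(Y = 1) = arm-specific constant + 0·M1 + ln(OR)·U

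The true mediator effect is zero. The quantity g is the shift in 1-month belief beyond baseline belief.

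**4. Approximate size by hand**, with q = 0.3:

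- Var(U) = 0.3 × 0.7 = 0.21; Var(M0) = 1 + 0.25 × 0.21 = 1.0525; Cov(U, M0) = 0.5 × 0.21 = 0.105
- Var(U | M0) = 0.21 − 0.105²/1.0525 = 0.1995
- Slope of U on M1 given T and M0 = 0.1995g / (0.1995g² + 0.85²)
- Spurious indirect effect ≈ 0.5 × ln(OR) × that slope

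For g = 0.6 and OR = 5, the slope is 0.1197/0.7943 = 0.151, and 0.5 × 1.609 × 0.151 = 0.121. For g = 0.3 and OR = 2, the slope is 0.05985/0.7405 = 0.081, and 0.5 × 0.693 × 0.081 = 0.028. For g = 0 it is zero.

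**5. Simulation of the same model.** Two arms of 212, uptake set at 7% vs 34%, q = 0.3, 600 trials per row. A false mediator is a product-of-coefficients 95% interval that excludes zero.

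| OR | g (SD) | Spurious indirect effect (log-odds) | False mediator, U omitted | False mediator, U included |
|---|---|---|---|---|
| 2 | 0 | −0.002 | 5.0% | 4.3% |
| 2 | 0.3 | 0.027 | 7.2% | 4.5% |
| 2 | 0.6 | 0.052 | 11.2% | 5.5% |
| 5 | 0 | 0.001 | 6.2% | 6.0% |
| 5 | 0.3 | 0.069 | 17.7% | 5.7% |
| 5 | 0.6 | 0.128 | 43.3% | 4.2% |

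The simulated effects agree with step 4. At q = 0.1 and g above zero, omission gives 5.7% to 19.2%. At q = 0.5, g = 0.6 and OR = 5 it gives 45.3%. With uptake at 3% vs 19% (q = 0.3, g = 0.3, OR = 5) it gives 14.0%. Simulation error near 5% is about √(0.05 × 0.95/600) = 0.9 percentage points.

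**6. Referral and intention omitted together.** Also 212 per arm and no true mediator effect, with 30% referred, uptake about 7-8% vs 19-22%, and 1,500 trials per scenario:

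| Assumed confounding | False mediator, both omitted |
|---|---|
| Weak: OR 1.5 for each, shifts of 0.1 SD | 6-8% |
| Moderate: OR 2.0 and 1.5-1.8, shifts of 0.15-0.2 SD | 13-26% |
| Strong: OR 2.5 and 2.0, shifts of 0.25-0.3 SD | 49-55% |

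With both variables included the rate is 4-5% throughout.

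**7. Measurement error alone.** If the confounders act only through baseline belief, but the scales have reliability 0.74-0.85, the spurious OR is 1.01-1.06 and false mediators appear in 4-7% of trials (800 trials per scenario). Noisy baseline scores do not by themselves create a large problem.

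**The case against.** The strongest reply is that adjusting for each mediator's own baseline may already be enough. If referral or intention works only through beliefs held at baseline, it is: the g = 0 rows show essentially no bias. Bias needs a further shift in 1-month beliefs, which the documents make plausible through the schedule but do not demonstrate or size. This stands, and it limits the point to a conditional one.

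Four other replies carry weight.

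- **Direction.** For fear, worry or defensive avoidance the sign of any referral effect is unknown, so confounding could shrink or reverse an estimate. A reader might infer that the reported indirect effects are inflated; the documents do not support that.
- **Partial coverage.** If intention is a mediator in the unlisted set, its 1-month value enters the uptake equation. In a check with 800 trials per scenario, adding only 1-month intention cut false mediation under moderate confounding from 17% to 10% (baseline intention acting directly on uptake) or from 12% to 5.5% (acting through 1-month intention). Under strong confounding the falls were from 50% to 23% and from 34% to 7%. This weakens the case for two of the three variables. It does not touch prior referral/awareness.
- **Missing covariates in the simulations.** None includes the ten SAP covariates, several of which may predict referral, so the rates are probably on the high side.
- **Few events.** At the SAP's 3% uptake, 212 women give 0.03 × 212 = 6.4 events in usual care or targeted print, and the uptake equation is already well filled. This argues for adding terms sparingly, not for leaving out a known common cause.

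Aim 3 is also secondary and partly exploratory. That lowers the stakes, but its mechanism claims still depend on this path. The allowance in section 6.1 for further adjustment where needed belongs to the Aim 1 model and does not extend the GSEM list.

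**Conclusion.** The point holds in conditional form. Prior CGRA referral/awareness is missing from the 6-month mediation model, although it is collected and cannot be covered as a mediator's baseline. Baseline recommendation and baseline intention are not listed, and may or may not be partly covered, depending on a mediator list that the SAP does not give.

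The consequence is that the indirect effect, and the split into direct and indirect parts, can be biased. This requires that the omitted variables move 1-month beliefs beyond baseline beliefs and also predict uptake. The false-mediator rate then runs from about nominal (6%) to about 50%, and returns to about 5% with adjustment. That range rests on assumed odds ratios, shifts and referral prevalence; it is not an estimate for this trial.

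Two stronger readings should be resisted. The documents do not show that the reported mediation is spurious. Nor is the primary comparison of uptake threatened: it and the total effect are protected by randomisation.

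**What to change.** In the third SAP item:

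1. Name the mediators in the GSEM.
2. Add baseline prior CGRA referral/awareness to every equation.
3. Add baseline CGRA intention and baseline provider recommendation wherever they are not already controlled as a mediator's own baseline, and enter them in the uptake equation as well as the mediator equations.
4. Code each as a single term, because uptake events are few.
5. Report the indirect effects with and without these terms, and base mechanism statements on the adjusted model.

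The cost is an SAP amendment of a few lines and a rerun, since the SAP describes this analysis as already done. No new data are needed. The downside is a few more parameters and slightly wider intervals. If the indirect effects hold, the Aim 3 claim is stronger; if they shrink, the report avoids naming a mechanism that the data do not support.

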2.2 Resources Available

A. Facilities

Cancer cases diagnosed in New Jersey will be obtained from the New Jersey State Cancer Registry (NJSCR), located within the Cancer Epidemiology Services (CES) program at the New Jersey Department of Health (NJDOH). The NJSCR is managed and supported by Rutgers Cancer Institute of New Jersey (CINJ) through a Memorandum of Agreement between the NJ Department of Health and Rutgers, The State University of NJ. NJSCR receives funding from the National Cancer Institute, the Centers for Disease Control, and other state and federal programs. The NJSCR is a population-based cancer registry dedicated to tracking the occurrence of cancer in the state of New Jersey since 1978. The NJSCR contains information on all cancer cases including the type of cancer, race, gender, age residence at diagnosis, first course of treatment, and survival and, has received recognition for its high quality and timely data. The CRP collaborates on and conducts cancer research studies, publishes findings in scientific journals, analyzes data from the NJSCR and produces statewide cancer incidence, mortality and other specialty reports that inform cancer prevention and control efforts.

The NJSCR employs a full complement of experienced cancer registration, research, and information systems personnel to successfully meet its goals for statewide cancer surveillance and research support. Research and data use are primarily managed and conducted by research scientists in the Cancer Surveillance Research Program (CSRP), under the leadership of the Director ([name]) and Deputy Director ([name]). The senior Research Scientists manage several research studies and participate in cancer control and prevention initiatives using NJSCR data. Investigators are required to work collaboratively with CSRP staff when developing a research protocol using NJSCR data. Staff members at NJSCR and CSRP are well trained in cancer registration and surveillance research

including patient contact studies. CES will support this project by providing key technical and research support for patient contact and provide critical content expertise to the research team in regards to cancer surveillance data and interpretation of results.

The physical location of NJSCR: [name] and [name]. Location of Data (Hosted by NCI contractors, remotely): Information Management System (IMS), Inc., TierPoint Baltimore Data Center [name].

Primary registry operations are located at the NJDOH, [name] where key card access to the building and registry space on the 1st floor is required. All visitors must be registered with building security. Per state policies, all cancer registry staff must display their state-issued ID at all times while on the premises. (Note: all employees hired through CINJ are issued state IDs upon employment.) Paper-based documents with identifiable data for cancer cases and employees are stored daily at the close of business in locked filing cabinets and drawers. Employees are also required to log- off or lock desktop computers when they step away from their workspace. The registry has staff working at the Rutgers-New Brunswick Campus in CINJ, [name], where key card access is also required and who follow the same procedures for securing paper-based documents with identifiable information and securing workstations as described above.

B. Medical Or Psychological Resources

Not Applicable

C. Research Staff Training

NJSCR staff involved in this study have been with CSRP for up to 5 years, and the majority possess a college or graduate degree. They attend regular trainings for phone interviewing and speaking with cancer survivors regarding NJSCR and study participation. All staff are trained on Confidentiality Procedures and are required to sign a confidentiality agreement annually. Study specific training will include:

1. The purpose and scope of the study;
2. Review of roles and responsibilities of each staff and NJSCR;
3. Review of the questionnaire;
4. Review of frequently asking questions.

